## **Elimination of Premature Ventricular Contractions in Heart Failure (EVAC-HF)**

Premature ventricular contractions (PVC) are the most common arrhythmia to be observed in the absence of structural heart disease, and 'frequent' PVCs are estimated to occur in 1–4% of the general population. Idiopathic PVCs are usually associated with a benign course from the standpoint of arrhythmic death, but may result in a cardiomyopathy that is reversible with suppression of the PVCs.

The concept that frequent PVCs might be responsible for the development of a cardiomyopathy was originally suggested following the observation that pharmacological suppression of frequent PVCs (>20,000/24 hour holter recording) in patients with dilated cardiomyopathy led to dramatic improvements in left ventricular (LV) systolic function and dimensions. Since that time, a number of additional reports documented a reversal of LV dilatation and impairment by both chemical and radiofrequency ablation (RFA), supporting the hypothesis that frequent PVCs (as few as 5,000 ectopic beats) might have a causative role in the genesis of LV dysfunction. A recent analysis of 174 patients found that a PVC burden of 24% best separated patients with >50% EF from <50% EF.

It is well documented that RFA is a safe and effective procedure in patients with symptomatic frequent ventricular ectopic beats and PVC-induced cardiomyopathy. Successful PVC suppression  $\geq 80\%$  of RV and LV PVCs has been reported to be as high as  $\sim 80\%$  using an ablation approach. Studies found improvements in LV dysfunction following ablation, and, notably, demonstrated a significant inverse correlation between EF and PVC burden before ablation, and a significant post procedural improvement in EF in 82% of patients who had abnormal systolic function before ablation. Improvement of the overall LV EF ranged from 13%-23% after PVC ablation. While the mechanism of PVC-induced cardiomyopathy is not clear, possible etiologies include asynchronous ventricular contraction generated by the PVCs, impaired calcium handling, or a decrease in calcium transient.

Previous studies have been limited to case reports and non-randomized, observational studies with variable, non-consistent adjunctive heart failure treatment. As such, the efficacy of RFA ablation above optimized medical and possible device therapy for heart failure with reduced LV function and frequent PVCs is still uncertain.

### **Justification:**

Frequent PVCs can be associated with cardiomyopathies and may be a target for therapy. To date, there have been no randomized, prospective trials to evaluate the efficacy of PVC suppression using RFA $\pm$ antiarrhythmic therapy in improving left ventricular systolic function compared to optimal medical therapy.

Consequently no unified treatment approach for these patients exist. While some physicians prefer aggressive PVC suppression using ablation procedures, other opt for intensive pharmacological heart failure treatment first. If the treatment effects observed in the observational studies of improvement of EF of ~15% could be verified in a randomized trial this would open a uniquely effective, new treatment strategy in this patient population.

### **Study Objective:**

EVAC-HF will be a prospective, multi-center, randomized study to assess if in patients with frequent PVCs (>20%) and non-ischemic cardiomyopathy (EF≤45%) PVC suppression of >80% using RFA and antiarrhythmic therapy results in an improvement of EF after 6 months compared to optimized medical therapy (OMT) alone. Patients and/or their physicians will be contacted for follow-up to assess symptoms, any hospitalizations, and obtain any study related procedure(s) documentation that may have occurred at 1 year and 2 years post enrollment.

Recruited patients will be randomized in a 1:1 fashion between continuation of stable optimal medical therapy alone (i.e. ACE-inhibitors/ARBs, beta-blockers, aldosterone antagonists, diuretics, and digoxin as indicated) and RFA ablation±antiarrhythmics plus OMT.

### **Study Population**

#### **Inclusion Criteria:**

1. Patients with reduced ejection fraction (EF ≤45%) demonstrated by transthoracic echocardiogram and deemed to be non-ischemic by nuclear stress test or cardiac catheterization.
2. Patients with >20% PVCs on 24 hour holter-recording
3. Patient is 18 years of age or older
4. Optimized medical therapy on stable therapy for minimum 3 months with no changes in beta-blocker, ACE-I/ARB, digoxin doses (varying diuretic doses permitted).

#### **Exclusion Criteria:**

1. Patients who are under the age of 18 years of age
2. Patients with >2 dominant PVC morphologies
3. Patients with cardiac surgery in previous 3 months or scheduled for following 6 months
4. Patients who were implanted with a biventricular device during the last three months or single/dual chamber device (with ventricular pacing >10%) during the last three months
5. Significant symptoms associated with PVCs that would make favor immediate ablation
6. Intracardiac mural thrombus or myxoma

#### Standard of Care Endocardial/Epicardial Ablation

Patients randomized to PVC suppression will undergo a clinically indicated, standard of care PVC ablation. The electrophysiology procedures will be performed according to the clinical standard of care in the respective institutions.

The following description is meant as a guideline, but will be modified according to the local expertise, best clinical care and outcome.

The ablation will be performed in the fasting state after informed consent is obtained. The PVC mapping will be performed using an endocardial and possibly epicardial ablation approach. Placement of the endocardial RV mapping catheters will be performed via femoral venous access. Mapping of the LV will be performed either via femoral arterial sheath and retrograde aortic access or via transseptal puncture. Epicardial access, if required, will be performed via a substernal, percutaneous puncture or a limited, surgically created epicardial access. Systemic heparinization to achieve an activated clotting time of 300s is performed for left-sided procedures. In the presence of frequent spontaneous ectopy, activation mapping might be performed with an open-irrigated catheter using a clinical three-dimensional mapping system. If the ectopy is infrequent, isoproterenol is administered. If PVCs remain infrequent, pace mapping can be performed at a pacing cycle length that matches the coupling interval of the spontaneous ventricular ectopy. RFA is performed at the site of earliest endocardial activation or best pace map. The energy is titrated to achieve an impedance drop of 10 ohms. The applications are continued for at least 30 s if adequate heating at the electrode-tissue interface is achieved. If the PVCs are abolished within 30 seconds, the energy application is continued for 60 secs and followed by another 60 sec application. If PVCs are still present after 30 secs, the energy application is terminated and mapping is continued after ablation of the PVCs, isoproterenol is administered at 2–10 mg/min as needed to shorten the sinus cycle length to 400 –500 ms to confirm that PVCs are not inducible by adrenergic stimulation. An effective procedure is defined as a reduction in PVC burden of 80%. In the event of pleomorphic PVCs, the dominant PVC morphologies will be targeted. VT induction is strongly encouraged (but not mandatory) during the PVC ablation. If patients with prosthetic valves are included the ablation approach will take this into account to minimize any possible negative effect on the valve function as determined by the local PI. Procedure success will be confirmed with a 24 hour Holter monitor during the first seven days after ablation therapy, which is standard of care after PVC ablations. If the goal of PVC reduction of  $\geq 80\%$  cannot be achieved with the initial procedure, then PVC suppression using either a repeat ablation procedure within 6 weeks of the initial procedure or a pharmacological approach with antiarrhythmics such as amiodarone, sotalol, dofetilide or dronedarone will be chosen for the duration of 6 months. If a PVC reduction of  $\geq 80\%$  cannot be achieved with a second ablation antiarrhythmic therapy will be chosen for the study duration of 6 months. Patients that had  $< 3$  continuous sinus beats prior to the PVC-suppressive therapy will undergo a clinically indicated TTE after PVC suppression to obtain accurate echocardiographic measurements.

### **Follow-up**

During regular clinic visits patients will be assessed for NYHA class and compliance with medications. Approximately six months after enrollment or the

last RF ablation a clinically indicated TTE and 24h Holter monitor will be performed.

All patients will undergo the following research interventions at the 6 months follow up:

- A **copy of anonymized clinical TTEs and Holter recordings** will be sent to the UMD echo core lab and UMD coordinating center.
- A second **blood draw** will be performed and sent to the UMD core lab.
- A second **6 MWT** will be performed.
- The patient will answer **heart failure questionnaires** (Kansas City cardiomyopathy as well as the Minnesota Living with Heart Failure Questionnaire and optionally SF12/36) after 6 months.
- If any additional clinical cardiac MRI has been performed an anonymized copy will be sent to the radiological core center at UMD
- Patients and/or treating physicians may be contacted for **clinical follow-up at 1 year and 2 years** post enrollment to assess for symptoms, hospitalizations and clinical events. It will be attempted to obtain any records from medical procedures that were conducted during that time such as but not limited to echocardiograms, Holter monitors, CT, MRI or cardiac catheterizations.

### **Risks:**

Ventricular tachycardia ablation procedures have a definite morbidity and mortality, with a major complication rate ranging from 2.5 to 6 %. This is due to both patient-related and procedure-related factors. Patients typically suffer from congestive heart failure and other comorbidities and the procedures are long, requiring the patient to lie flat for up to eight hours at times.

In addition to the risks of sedation, standard risks of an endocardial procedure include bleeding and other vascular access complications, stroke, myocardial infarction and rarely myocardial rupture and pericardial tamponade, aortic valve avulsion, and entanglement of the catheter in the mitral valve apparatus requiring surgical intervention, and death. The safety data of PVC ablations is not as well established as for VT ablations. In general, significantly less ablation lesions have to be applied frequently reducing the procedure time and volume administered. Additionally, many PVC ablations can be performed from the RV resulting in less risk of thromboembolic events or groin complications than for left-sided ventricular tachycardia ablations.

Epicardial ablations will have to be performed in a subgroup of patients. This approach has been associated with complications such as RV perforation, coronary artery or phrenic nerve injury or abdominal bleeding.

There are no known significant risks associated with echocardiograms or Holter monitors. There is a slight possibility of skin redness or irritation due to the

placement of the ECG electrodes, which should disappear within several hours of removing the electrodes.

Blood drawing can cause pain, bruising, lightheadedness and, on rare occasion, infection.

There are risks of loss of confidentiality to patients that participate in this trial; however all necessary precautions will be taken to assure the patient's confidentiality is maintained. The information will be kept in secure locations. In any publication or presentation of research results, patient's identity will not be disclosed.

Pregnant females are excluded from participation in this trial because they are not eligible for catheter ablation due to radiation risks to the developing fetus. All females with child bearing potential that want to participate will need to do a pregnancy test the morning of the ablation procedure, and the test must be negative to have an ablation.

Specific data to be collected:

- 1- Patient demographics (not identified)
- 2- Peripheral blood samples will be collected and stored from the time of randomization and at 6 months. These samples will be sent to core laboratory and assayed for relevant biomarkers including BNP, galectin-3, soluble ST2.
- 3- Blood samples will be collected at initial visit for genome analysis
- 4- Echocardiographic and electrocardiographic data
- 5- 24 hour Holter recordings with available HRV data
- 6- Procedural data such as 3-dimensional left ventricular mapping data including number and origin of PVCs and the successful ablation sites
- 7- Peri-procedural data collection including mode of sedation, inducibility, dose of sympathomimetic drugs, procedure duration and fluoroscopy time
- 8- The complications, if any, of the procedure
- 9- The acute and intermediate-term success rate of the procedure.
- 10- Procedure, medication and outpatient visit costs
- 11- 6 MWT at baseline and 6 months
- 12- Heart Failure Questionnaire at baseline and 6 months
- 13- Clinically performed high-resolution CMRI studies performed prior to the enrollment, during randomization duration and after 6 months will be collected to assess anatomic, perfusion and delayed enhancement myocardial fibrosis.
- 14- Tissue samples that may become available during the study duration from clinically indicated procedures such as biopsy, LVAD placement or heart transplantation will be stored for further tissue analysis

15-Clinical data such as past medical history, medications, NYHA class, physical exam findings, hospitalizations will be assessed during the 2-years follow-up

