**Elimination of Premature Ventricular Contractions in
Heart Failure (EVAC-HF)**

NCT 01757067

9-17-2011

Elimination of Premature Ventricular Contractions in Heart Failure (EVAC-HF)

Data Analysis

Primary Endpoint

Left ventricular ejection fraction

Based on previous observational data, a minimum 10 percent improvement of EF is expected with successful reduction of PVC burden. We expect a successful suppression of $\geq 80\%$ of PVC's in 60% of patients. We assume an attrition rate of 10% without 6 months follow-up data (in those cases of missing data the enrollment EF will be used as 6 month EF as well). As a result we expect a $10\% \times 0.6 = 6\%$ change of EF, which after accounting for a 10% attrition rate results in a $6\% - 0.6\% = 5.4\%$ improvement of EF in the intervention group. The standard deviation for echocardiographic LV assessment is assumed to be 7 percent. As primary intention-to-treat analysis, we propose a pilot study with 80 percent power to detect a 5.4 percent improvement in LV systolic function (LVEF at 6 months – LVEF at baseline) between the two groups, at an alpha level of 0.05. Using a 1:1 randomization, we will need to randomize 56 patients (28 in each arm) to complete our assessment. Each study site will be allowed up to 10 participants. Randomization will be assigned via email contact with the coordinating site, University of Maryland Medical Center. The Permuted Block design will be utilized in assuring even distribution to the 2 arms of the study.

Fixed Scenario Elements	
Distribution	Normal
Method	Exact
Group 1 Weight	1
Group 2 Weight	1
Number of Sides	2
Null Difference	0
Alpha	0.05

Computed N Total					
Index	Mean Diff	Std Dev	Nominal Power	Actual Power	N Total

9	5.4	7	0.8	0.809	56
---	-----	---	-----	-------	----

A prespecified “on successful treatment” analysis will be performed comparing patients with successful $\geq 80\%$ PVC suppression with patients with unsuccessful PVC suppression.

In case of missing data due to loss of follow-up the enrollment EF will be used as the EF at 6 months assuming no improvement.

Patients in the OMT group that had to cross-over to the ablation group will be analyzed in the OMT group for the intention-to-treat analysis.

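### Antiarrhythmic drugs belong to the randomised strategy, but structured safety collection is worded for the procedure only and the Risks section names no drug risk

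*Protocol*

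**What the plan says.** **The strategy.** The protocol's Study Objective and the SAP's Secondary Endpoints both define the intervention as ablation with or without antiarrhythmics. Under Standard of Care Endocardial/Epicardial Ablation, a patient whose first procedure misses 80% suppression goes either to a second ablation within 6 weeks or to "a pharmacological approach with antiarrhythmics such as amiodarone, sotalol, dofetilide or dronedarone will be chosen for the duration of 6 months". If the second ablation also misses, "antiarrhythmic therapy will be chosen for the study duration of 6 months".

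**The safety record.** Item 8 of the list of data to be collected, identical in the two documents, reads "The complications, if any, of the procedure". No other item is worded as safety. Item 10 collects medication costs, but no item collects medication harms.

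**The Risks section.** It covers ablation, sedation, epicardial access, blood draws, confidentiality and pregnancy. It even comments on the tests ("There are no known significant risks associated with echocardiograms or Holter monitors") and mentions skin irritation from electrodes. It does not mention antiarrhythmic drugs.

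**Other data.** Items 4 and 5 collect ECG, echo and Holter data. Item 15 is an open list of clinical data over 2 years that includes medications, examination findings and hospitalizations. The Follow-up section adds a 1- and 2-year contact about symptoms and clinical events, worded there as something that may happen. For regular clinic visits it lists only NYHA class and medication compliance.

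**The SAP.** Its endpoints are echo measures, biomarkers, the 6-minute walk and questionnaires. It has no adverse-event definition and no safety analysis.

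**The concern.** A site that follows item 8 as written records a groin bleed. It has no place to record bradycardia, an arrhythmia, organ toxicity or a drug stopped for intolerance when these arise on a drug that the study pathway itself prescribes. What is not recorded in structured form during the 6 months cannot be recovered reliably at analysis.

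The trial would then report the EF effect of a combined strategy beside structured harm data for only one of its components. Item 8 also cannot support a comparison of harm by arm, because an OMT patient who has no procedure has nothing to enter under it. Drug exposure is nevertheless possible in that arm: patients already on stable antiarrhythmics are eligible (Enrollment), and the SAP allows for a rare start during the randomised period.

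**Working it through.** **1. The plan's own figure.** The SAP plans "80 percent power to detect a 5.4 percent improvement in LV systolic function", "at an alpha level of 0.05", two-sided, with SD 7 and 28 patients per arm. An exact two-sample t calculation with standardised difference 5.4 / 7 = 0.771 gives 27.37 per arm. That rounds up to 28 per arm, or 56 in total, with power 0.809. The figures reproduce, and nothing in this point alters them.

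**2. How many ablation-arm patients would newly take a drug.** The SAP expects suppression of at least 80% "of PVC's in 60% of patients", without saying at which step of the pathway. The protocol's background cites success of up to about 80% for ablation. With 28 patients:

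| Reading | Formula | Patients |
|---|---|---|
| 60% is the final success rate of the strategy | 0.40 × 28 | 11.2, plus those whom a drug brings to target |
| 60% is first-ablation success, every miss takes a drug | 0.40 × 28 | 11.2 |
| 60% applies independently to each ablation, every first miss is re-ablated | 0.40 × 0.40 × 28 | 4.5 |
| About 80% at first ablation, every miss takes a drug | 0.20 × 28 | 5.6 |
| About 80% applies independently to each ablation, every first miss is re-ablated | 0.20 × 0.20 × 28 | 1.1 |

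The first reading fits the SAP best, because the SAP multiplies 0.6 by the expected EF gain for the whole arm (10% × 0.6 = 6%). Under it, about 11 is a floor if sites follow the pathway: anyone still below 80% has by then reached the drug step.

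**3. What such numbers can show.** If no event is seen in n exposed patients, the one-sided 95% upper bound on the event rate is 1 − 0.05^(1/n). For n = 11 this is 23.8%; for n = 4 it is 52.7%. The data can be described but cannot establish drug safety, so a test is not worth adding.

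**4. What each data source would hold on drug harm.**

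- *Item 8:* procedure complications only.
- *Items 4 and 5:* could show an arrhythmia or bradycardia on a tracing; no drug-safety purpose or analysis is stated.
- *Item 15:* medications, findings and admissions; no event definition and no attribution to a drug.
- *Clinic visits within 6 months:* compliance, which may reveal a drug stop; adverse effects are not listed.
- *1- and 2-year contact:* symptoms and events, but after the cross-over that the Enrollment section plans at 6 months, so they are hard to assign to the randomised arm.

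Across these sources, no event is defined, related to a drug or carried into an analysis.

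**The case against.** The best defence is that general data collection is wider than item 8 suggests. Item 15 is open-ended and runs 2 years, tracings can show rhythm events, compliance is checked at visits, and all of this applies to both arms. That stands, and it rules out several stronger readings.

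- *Drug harm goes wholly unrecorded, or is seen only on admission.* A reader might infer this from item 8. The other sources above would catch some of it, in OMT patients as well. The gap is in structure, attribution and analysis.
- *Every patient who misses 80% gets a drug.* Repeat ablation is an alternative after a first miss; the drug is the sole route only after a second.
- *Some 40% of the arm will be exposed.* This follows from one reading of the 60%. Other readings give far fewer.
- *Exposure falls on those least likely to gain EF.* The SAP does say that these drugs often fail to suppress PVCs. But a patient brought to target by a drug counts as a success, and the background cites EF improvement under pharmacological suppression. It may hold for some patients, not in general.
- *Patients are not told about drug risks.* The consent pages are not available here, so the point is limited to the protocol's Risks section.

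A further fair objection concerns the remedy. An item for procedure complications plus drug events would look harder for harm in the ablation arm than in the OMT arm, where clinical deterioration would still have no adverse-event item. This is right, and it shapes the fix.

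**Conclusion.** The point holds in this form: drug-related harm of a prespecified part of the strategy is not set up for structured collection, attribution or reporting by arm, and the protocol's Risks section does not describe it. General data may catch some of it. The number newly exposed in the ablation arm lies between about 1 and 11 or more of 28, depending on where in the pathway the 60% or 80% applies, on independence between two ablations, and on how sites choose after a first miss. The gap exists anywhere in that range, because the pathway is prespecified and its harm is not. It should be closed. It does not affect the primary endpoint, the sample size or the power.

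**What to change.** 1. In both documents, replace item 8 with: *complications of the procedure and all adverse events, in both arms, from randomisation to the 6-month visit, with relation to ablation or antiarrhythmic drug, and drug start and stop dates and reason for stopping.* Collect this in the same way in both arms.
2. Add to the SAP a descriptive summary of these events by randomised arm, without a test. Give all events first and attributed events second, since treatment is open to those who attribute. Record event dates: the 6-month assessment may be timed from the last ablation, so follow-up can run longer in the ablation arm.
3. Add antiarrhythmic drugs to the protocol's Risks section.

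Ending at the 6-month visit keeps the comparison within the randomised period, before the planned cross-over. Later events can still be listed from the existing 1- and 2-year contact.

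The cost is one more case-report-form section, a short SAP paragraph and a Risks paragraph. The reported harm rate of the intervention may look less favourable. No change to drug choice, dosing or any clinical rule is proposed.
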